1.1 Background

1.1.1 Paroxysmal Atrial Fibrillation (AF)

Paroxysmal AF is a common arrhythmia that impairs the lives of otherwise healthy, high-functioning individuals. AF is the most common arrhythmia, has a lifetime risk of 1 in 4, and is expected to affect 16 million Americans in 2050.¹ Each year, AF is responsible for >100,000 strokes, >400,000 hospitalizations, and >\$6 billion in direct health care expenditures.¹⁻⁵ Paroxysmal AF patients have a similar or worse quality of life than patients with heart failure or myocardial infarctions.⁶ To help alleviate the related debilitating symptoms, the American Heart Association (AHA) and other cardiology societies recommend potentially lethal drugs and invasive procedures to reduce AF episodes.⁷ Prevention and treatment strategies that are lower risk, lower cost, and more directly under patient-control are needed.

Studies have identified risk factors for new onset AF; however, triggers for discrete episodes have been largely ignored. Behaviors or exposures that may trigger AF episodes have not been studied systematically, but clinical experience, anecdote, and patient reports suggest that personal behaviors (e.g., sleeplessness, stress, caffeine) may trigger AF. Several studies suggest that alcohol may be an acute trigger for AF episodes.^{8,9} If triggers could be identified, they might be avoided, providing a strategy to effectively prevent AF. To our knowledge, no previous study has examined if triggers affect AF episodes, demonstrating the profound disconnect between previous research and the interests of the patients suffering from AF. If AF episodes can be manipulated based on personal decisions, a new, inherently patient-centered paradigm in the treatment and prevention of AF may be achieved.

1.1.2 A Critical Research Gap

Identification of AF triggers (the "trigger wars") is a top priority among AF patients. Patients participating in online forums and focus groups frequently discuss what particular factors trigger AF episodes. [name], CEO of StopAfib.org, refers to these common online discussion as the "trigger wars". It is thus not surprising that identifying factors that trigger AF episodes in particular individuals using single subject study designs emerged as a key research

priority at the 2014 HeH Patient-Powered Research Summit, a research brainstorming session attended by nearly 100 patients, researchers, clinicians and other stakeholders. During this conference, an exercise allowed patients to communicate what they believed to be the most important issue in their disease. Common themes were identified and patients were divided into interest groups – one organically formed around AF. Members of the AF interest group identified individual-level triggers for the AF episodes as their highest research priority, After learning about the concept of mobile technology enabled N-of-1 trials, the AF interest group worked with content and clinical research experts to develop a study idea to test if an N-of-1 approach to identifying and elimination of AF triggers would improve AF outcomes.

1.1.3 Potential for the study to improve health care and outcomes

Using N-of-1 methods to help AF patients identify the best treatment will shift the clinical paradigm towards a more personalized and patient-centric approach to this important disease and provide patients with individualized data about the effectiveness of trigger modification in controlling symptoms. Rigorously applied trials will convince the evidence- focused cardiology community that triggers of AF differ between individuals and carry value. Modern technology and devices that are now so ubiquitous allow implementation of personalized N-of-1 studies in large populations with AF. This extremely common arrhythmia, that has few effective treatment options and yet might be readily manipulated by patients themselves, is ripe for this novel approach.

1.1.4 Study Setting

The study will take place remotely using an internet-based system produced at the University of California, San Francisco within the Health eHeart Alliance Patient Powered Research Network and will leverage the resources available in the Health eHeart Study, a web-based cardiovascular cohort study that enables remote consent, electronic data capture system (Eureka--please see technology platform configuration 1.3.1), and integration with devices and apps. To date, the Health eHeart Study has enrolled > 91,000 individuals from around the world, with >4,700 participants with atrial fibrillation.

1.2 Study Objective

Test the comparative effectiveness of N-of-1 trials versus data tracking alone to identify and eliminate individual- level triggers and reduce AF frequency and severity.

1.3 Technology Platform

1.3.1 Technology Platform Configuration

Eureka: The Eureka Research Platform is a digital research platform developed at the University of California San Francisco as part of a cooperative agreement with the NIH. The purpose of the platform is to facilitate mobile health research for any interested investigator. The Eureka platform includes a participant-facing "front end," an investigator portal, a secure "back end" for data storage and analyses. The platform is designed as an all-inclusive, configurable, easily-scalable research platform, inclusive of all aspects of research-from participant enrollment, onboarding and consent, to multi-modal data collection, study administration/management and data extraction. The platform's front end can be customized by individual investigators to implement their specific research project. Existing functionality includes the ability to obtain remote consent (although in-person consent can also be used), deploy participant surveys, message participants via push notifications, texts, or emails, integrate with external apps, sensors, and Bluetooth enabled devices, and capture data collected from smartphones (such as HealthKit data, geolocation data, accelerometer/ activity data). The investigator portal provides a secure website wherein investigators, coordinators or other individuals with appropriate permissions can visualize relevant participants' data and study status. The back end of the Eureka platform is a multi-tenant system that enables data collection, management and storage derived from multiple sources and from studies of various forms. This architecture rests on a secure and HIPAA-compliant AWS cloud with the capacity to curate dense data from more than 1 million participants. In addition to providing data as needed to investigators, the infrastructure houses a de-identified data repository that is publically available to help fulfill the general mission of advancing science and wellness.

Eureka will configure a study-specific version of the platform to collect data required to execute the research proposed in this study. Study participants will use the Eureka N-of-1 platform (website and mobile app) to collect outcome data, track intervention/exposure status, and review collected data in real time. Upon trial completion, Eureka will present N-of-1 results to patients randomized to N-of-1 trials with easy-to-understand graphics that include probabilistic assessments of the benefits of the intervention.

As part of design sessions held prior to enrollment, members of the research team, including patients and clinicians, provided input regarding the study-specific configurations of the Eureka platform. Study specific configurations will include: (1) trial specific onboarding page, (2) study library to generate and perform analyses of trials based on a trial-specific template, (3) server workflow that automates execution of the personal trials, and (4) customization of the user interface for prompts, reminders, forms, surveys, and visualizations. Final configurations will depend on input from key stakeholders. Technology modifications will be done via iterative, rapid development and testing cycles with a firm completion deadline by month 6 of this study, prior to patient enrollment.

AliveCor: AliveCor is a mobile electrocardiogram (ECG) monitoring app that pairs with a smartphone case to enable single lead ECG recordings. To date, >1,000 HeH participants have successfully downloaded this app and fitted the smartphone case, and all have done so remotely using the same work-flows that would be used for the current proposal. The AliveCor device includes an FDA-approved, patient-facing algorithm to detect AF episodes. A connectivity wizard already developed for the Eureka portal will enable linking the AliveCor monitoring to study data. This Eureka integration will allow the study to receive data from the AliveCor device and can be used as validation of atrial fibrillation episodes.

1.4 Study Design

This is a randomized controlled trial that examines the comparative effectiveness of N-of-1 study protocols vs. symptom surveillance (data tracking alone) for reducing AF episode frequency and severity (Figure 1). Throughout the duration of the study, all study participants will use the Eureka mobile app to self-report daily mood and sleep quality, AF episode duration (in minutes) and severity, and will use the AliveCor mobile electrocardiogram (ECG) to record ECG tracings. Participants will be instructed to take ECG tracings at least once per day as well as any time they think they are having an AF episode. Participants will be able to visualize their data in real time and will receive weekly summaries of their AF frequency and severity via Eureka. Due to the rapid growth and availability of mobile apps and devices that can monitor AF episodes, we believe the symptom surveillance condition is a realistic and appropriate comparison group.

[figure not shown]

Figure 1: Study Design

In addition to tracking mood, sleep and AF data, participants in the N-of-1 trial arm of the study will also test their triggers and track their trigger exposure. N-of-1 trials will be conducted using a

citizen health-scientist approach where patients are empowered and supported in independent experimentation. Together with the HeH Alliance Patient Advisory Board (PAB), the study team designed a menu of triggers that participants will select from to test in their personal AF triggers in a rigorous testing environment. These N-of-1 trials will consist of 6 randomly assigned periods of exposure (trigger exposure/trigger "on") and elimination (avoiding trigger/trigger "off").

1.4.1 Interventions and Comparators

N-of-1 Trial arm: Participants will use the Eureka mobile application and AliveCor device to execute at least one N-of-1 trial with the goal of identifying and better controlling their AF triggers. Each N-of-1 trial will last a total of 6 weeks and will include up to 3 periods of trigger exposure and 3 periods of trigger elimination with each exposure/elimination period lasting 1 week. Participants will be randomly assigned to start their trial with a period of either trigger exposure or elimination. During each N-of-1 trial, participants will track daily AF duration and severity, daily mood and sleep quality, daily AliveCor tracings and daily trigger exposure. At the end of each trial, participants will be able to review their trial results which will include visualizations of their daily AF symptom and trigger tracking over time. After completing a trial, participants will be instructed to implement any lifestyle changes they deem appropriate based on what they learned from the results of their trial. Participants will implement these changes for a period of 4 weeks during which they will continue to track AF episode duration and severity via the app. At the end of the 4-week lifestyle change period, participants will complete the Atrial Fibrillation Effect on QualiTy of Life survey (AFEQT) (Appendix A) and will then have the option of testing another trigger or ending their study participation.

Symptom Surveillance arm: Participants will use the Eureka app and AliveCor device to record daily AF duration and severity, daily AliveCor readings and daily mood and sleep quality for a period of 10 weeks. Participants will be able to visualize their AF, sleep and mood data in real time and will receive a weekly summary of their data via the Eureka app.At the end of the 10-week data tracking period, participants will complete the AFEQT survey and will then have the option of either ending their study participation or crossing over to the N-of-1 trial arm to test their triggers.

1.5 Study Procedures

Randomization/Baseline evaluation: Potential participants will be identified via the Health eHeart Study and the StopAfib.org patient advocacy organization and reached out to via email campaigns. Of note, invitations will be extended broadly to include friends family and acquaintances of those participants. Patients may also be recruited directly from UCSF clinics or other web-based sources of potentially interested atrial fibrillation patients. The study email campaign will contain an overview of the study. If the patient is interested in participating in the study there will be a link for the participant that will take them to the mobile app store to

download the Eureka app. Potential participants will be prompted to register an account and will complete an inclusion/ exclusion criteria survey within the Eureka app. If eligible, they will continue on to the study consent form (Appendix B). Upon completion of the electronic study consent, Eureka will randomize participants to either the N-of-1 or the symptom surveillance arm of the study with a 1:1 allocation ratio.

Participants will then be asked to complete baseline data collection which will include basic demographics, medical history, and current atrial fibrillation medications. After baseline data collection, the study team will ship AliveCor devices to study participants over a period of two weeks. At the end of this two week period, participant will be prompted to visit the Eureka application to complete a device consent and then will be instructed to download the AliveCor app and link their AliveCor device to their Eureka account. All participants will then complete the Atrial Fibrillation Effect on QualiTy of Life survey (AFEQT) (Appendix A). Once they complete the survey, the app will show participants which study arm they have been randomized to and prompt them to begin the appropriate study activities.

Experimental arm: Participants randomized to the N-of-1 study arm will test AF trigger(s) (ie. diet, exercise, sleep, alcohol, smoking, certain exercises, etc). Using a menu of options in Eureka, participants will select a trigger to test and then will be randomly assigned to start with a period of trigger exposure or elimination. Each exposure/elimination period will last 1 week and each trigger will be tested for a total of 6 periods with 3 weeks of trigger exposure and 3 weeks of trigger elimination. During each testing period, the Eureka app will send participants daily reminders of the behavior that is required, specifying quantity and type of trigger exposure/elimination when appropriate. For example, if the trigger is alcohol consumption, this might include a daily alert that reads:

Elimination week: "This week, AVOID your trigger: **ALCOHOL**. Avoid drinking any alcohol. **3** more days left of AVOIDING alcohol this week."

Or, alternatively:

Exposure Week: "This week, TEST your trigger: **ALCOHOL**. Go ahead and consume alcohol this week. **3** more days left to TEST your trigger this week."

During the testing period, participants will also receive daily reminders prompting them to go to into the Eureka app to complete study activities. Participants will be asked daily about the estimated total duration and severity of their AF episode(s), mood and sleep quality and trigger exposure (e.g. "How many alcoholic drinks did you have yesterday?"). They will also be prompted to take daily AliveCor readings. Participants will be instructed to take ECG tracings at least once per day as well as any time they are experiencing AF symptoms. Following the completion of their N-of-1 trial, participants will be able to view their trial results and interpretations on the Eureka app. Once their N-of-1 trial is complete, participants will stop receiving reminders about trigger exposure/elimination and trigger tracking but will be prompted

to continue to track their AF frequency and severity for 4 more weeks. During this 4 week period, participants will be able to implement any lifestyle changes they deem appropriate based on what they learned from their N of 1 trial. Following the completion of the 4 week "lifestyle change" period, participants will complete the AFEQT survey and will then have the option of either testing another AF trigger or concluding their study participation. Participants that choose to test additional triggers will have up to one week to start their next N-of-1 trial that will follow the same trigger testing protocol as the first. Participants will have the option of testing up to 5 triggers following this protocol.

Symptom Surveillance: Participants randomized to the symptom surveillance arm will engage in data tracking for a period of 10 weeks and receive daily reminders to complete study activities. Participants will be asked daily about the estimated total duration and severity of AF episode(s) and daily mood and sleep quality. They will also be asked to take AliveCor readings at least once per day and anytime they are experiencing AF symptoms. Participants will be able to visualize their AF data in real time and will receive a monthly summary of their AF frequency and severity via the Eureka app. At the end of the 10-week tracking period, participants will complete the AFEQT survey. Then, participants will have the option to cross over to engage in trigger testing. Participants that choose to test their triggers will be able to test up to 4 triggers, one trigger at a time, following the N-of-1 trial protocol described above.

1.5.1 Outcome Measures

The primary study outcome is change in quality of life, measured by the AFEQT, between those randomized to N-of-1 experiments versus those that tracking their data alone. Secondary outcomes will include results of individual-level N-of-1 trials.

1.6 Participant Selection and Withdrawal

At least 478 AF patients will be recruited to participate remotely in the RCT.

1.6.1 Inclusion Criteria

- (1) symptomatic paroxysmal AF
- (2) a smartphone

1.6.2 Exclusion Criteria

- 1. Non-English speakers
- 2. Children (age < 18 years)
- 3. Patients with plans to substantially change AF management (such as with ablation or change in antiarrhythmic drugs) over the ensuing 6 months
- 4. Unwillingness to test AF triggers.
- 5. Patients who have had an AV node or AV Junction ablation

1.6.3 Participant Pre-screening and Recruitment

Participants will be recruited primarily from two sources: (1) the Health eHeart Study, which has >4,000 well-characterized AF participants who have consented to be contacted via the internet about other studies and which recruits >1,500 new participants (58 AF patients) per month; and (2) StopAfib.org, a patient-run website with 765,000 unique visitors, 2.2 million pageviews in 2014 and a mailing list of 13,000 engaged AF patients. Those participants will also be recruited as "ambassadors for the study by inviting others they know that might be interested. Patients may also be recruited directly from UCSF clinics or other web-based sources of potentially interested atrial fibrillation patients. Participants recruited directly from the Health eHeart Study will be emailed by the Health eHeart study team. We will plan to email the Health eHeart Study participants who have indicated they have AF. Participants recruited from StopAfib.org will receive a similar email with a link to the mobile app store. Potential participants will then be prompted to register an account, consent for the study then complete an inclusion/ exclusion criteria survey within the Eureka app.

1.6.4 Early Withdrawal of Participants

Study participants can opt out of testing a trigger or withdraw from the study at any time of their choosing without penalty.

1.7 Statistical Plan

1.7.1 Sample Size Determination

We conservatively estimate that the available pool will include 10,000 engaged individuals meeting the inclusion and exclusion criteria. Given that we estimate that 478 participants will be needed, we need to consent only 5% of eligible patients. Strategies to overcome barriers to enrollment include continuing aggressive efforts to recruit large numbers of HeH participants (in collaboration with the HeH Alliance and partners such as the AHA) and ongoing messaging from the CEO and other leadership encouraging enrollment to StopAfib.org participants and visitors (Std PC-2). In order to achieve at least 478 patients that complete the 6 month study, we will aim to initiate at least 600 patients.

Sample Size & Power Calculations: As those with at least moderate AF severity have an AFEQT score of 58 ± 1958 and the most modest of therapies typically improves this score by a mean of 5-10, we have powered this study conservatively to detect an improvement of 5 points in the AFEQT. We estimate 239 patients in each group would provide 80% power to detect this small, yet still clinically meaningful difference. Given the enthusiasm of >1000 AF patients already engaged by the investigators, we believe enrollment will not pose a challenge.

1.7.2 Statistical Methods

Analysis of Individual N-of-1 Trials: At the end of each person's N-of-1 trial, statistical analysis will be performed to compare results on the two treatments. Each N-of-1 trial requires a separate analysis which is automated to run in the background once each trial is completed. The analysis consists of running Bayesian models that make different assumptions about the nature of the data (e.g., data with and without correlation over time, with and without carryover across interventions). Models will incorporate the appropriate scales for the outcomes (e.g. normal distributions for continuous variables, multinomial distributions for categorical variables) and the appropriate representation of the function linking the expected outcome to the predictors (e.g., cumulative logit link for ordinal outcomes). The results of these models will be automatically compared to determine which best fits the data and the simplest model that accurately fits the data will be chosen using appropriate model selection criteria such as the deviance information criterion. Each patient will be provided with an estimate of the (1) treatment difference, and (2) probability (or likelihood) that each treatment is the best for a particular outcome. Results will be portrayed numerically and graphically. We will develop educational materials to aid patients in interpretation. Posterior probabilities of outcomes will be calculated using an interface that incorporates open-source R software interfacing through Riags with open-source JAGS software.55 The R code creates the Bayesian model, loads the stored data and chooses intelligent starting values that are then fed into JAGS to return the Markov chain Monte Carlo (MCMC) simulations of the joint posterior distribution. The R package will accept input from Orchestra to construct models. The statistical methods used are being applied currently in another N-of-1 study and will be adapted as necessary to create a connection between the R code and Eureka..

Meta-Analysis of N-of-1 Trials: The collection of individual N-of-1 trials can be thought of as a set of studies whose results can be combined as in a meta-analysis. The data can be considered as a multilevel structure in which a set of patients is studied with each patient having a set of measurements. Standard multilevel mixed model methods will be used to estimate the average effect and variance within and across patients. Across patient values estimate the average effect in the population of patients studied, while the within-patient estimates describe an improved estimate of each patient's true effect assuming exchangeability across patients. We will fit these models using a Bayesian multilevel model with non-informative priors in order to obtain posterior distributions of the within and between effect sizes. We will then compare the multilevel patient estimates with those from the patient's data alone in order to determine how much the effects change and how much additional precision these estimates gain.

Analysis of Comparative Effectiveness: The experimental design is a simple two-arm randomized trial comparing N-of-1 vs. symptom surveillance. The primary outcome is the change in the AFEQT scale from baseline to 12 weeks. The mean change in each treatment group will be compared by a t-test. The average frequency and severity of AF episodes per week during the final month of each participant's enrollment will be the secondary

outcomes. Their group means will also be compared with a t-test. We will check for balance in covariates across the randomized groups and will adjust for any imbalances by including those covariates in regression analyses and reporting the adjusted treatment effect as a secondary analysis.

Missing Data: A major purpose of this aim is to determine the feasibility and usability of N-of-1 studies for actual application in clinical practice. Therefore, carefully documenting adherence and completion rates and predictors of each will be an important aspect of this study. Within the HeH study, we have found that >90 % of all AF HeH study participants complete all AF-related surveys, including the AFEQT. The primary analysis will be intent-to-treat which uses all participants as randomized. When no endpoint is available, we will assume no change. Further analyses will employ multiple imputation to fill in missing values, particularly in covariate-adjusted models ([name]-3).

Heterogeneity of Treatment Effects (Std HT-1 through 4): HTE between individuals with AF is a major issue that is of particular interest to patients. In secondary analyses, we will test for interactions between treatment and covariates that describe potential pre-specified HTE hypotheses. Predetermined interaction analyses will include testing for effect modification by "lone" AF (age <65 years of age without any cardiovascular risk factor) vs. not, sex, and race (non-Hispanic white race vs. not). Additional post hoc interaction analyses examining currently unrecognized moderators will be planned based on input from patients over the course of the study. These are likely to include testing for effect modification by particular triggers (e.g., setting an early bedtime works well whereas avoiding morning endurance exercise does not). Statistical significance for interaction analyses will use a p-value cut off of \leq 0.01.

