5.1 Overview

Figure 2 details the study design for Aim 2 which is designed as an RCT to compare use of N-of-1 studies vs. symptom surveillance (data tracking alone) using comparable mHealth technology in both study arms. Working with the HeH patient stakeholders, we will design a menu of triggers that people with AF may select to test in their own personal N-of-1 study. This menu will include approaches for modifying triggers including alcohol, caffeine, exercise (frequency and intensity), sleep, liquid intake/dehydration,

meal size, sleep position (e.g., lying on left side), beverage and food temperature, or choices at the option of the patient. These N-of-1 protocols will involve 6 randomly assigned treatment periods (each 1-week in duration) of exposure (trigger "on") and elimination (trigger "off").

Figure 2

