5.4.2 Analysis of Individual N-of-1 Trials

We will analyze each patient's trial of a specific trigger using the same methods as in Aim 1 applied to the outcomes of frequency, severity and duration of events reported daily. Frequency will be analyzed as a binary event on each day. Severity and duration will be analyzed as a mixture model between non-event days and event days with the mixture probability corresponding to the probability of an event.

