5.4.3 Meta-Analysis of N-of-1 Trials

We will conduct separate meta-analyses of each set of N-of-1 trials that test a particular trigger. We expect this will likely be most relevant to the triggers offered in the menu which patients are more likely to try and which were also the most commonly identified triggers in a survey recently sent to 1,000 AF patients. The meta-analyses will use the same Bayesian multilevel methods as those outlined in Aim 1 and will be applied to the outcomes of AF events, duration and severity as well as the safety endpoints listed in Table 2. We will use distribution and link functions appropriate to the scale of each outcome variable. We will calculate the average treatment effect in the group of patients as well as the individual effects adjusted for the other patients.

Patients with AF are particularly interested in whether certain triggers are more likely than others to induce AF. Because patients in this study will be choosing to study different triggers and often will be conducting more than N-of-1 trial, the set of trigger comparisons will form a network of triggers (plus no trigger) that may be analytically compared using methods of network meta-analysis.²⁵ Triggers may then be compared indirectly through the common control using techniques from network meta-analysis. The complicating factor here is that trials done by the same patient will be correlated and it will be necessary to adjust for this correlation in the network meta-analysis model. This can be done in two different ways. The first would be to treat each patient's trials as separate and introduce a common patient effect into a Version 1.0 5/12/17

mixed model. The second would be to combine all the trials for a patient into one trial with several arms, one for each different trigger and one for no trigger that would combine all the results from the no trigger arms. If a patient changed the control (no trigger) arm in a new trial (e.g., by testing two triggers vs. one trigger), then the control arm would be analyzed according to the trigger used. This approach would create multi-arm trials for patients with multiple trials. These would then be analyzed by methods for multi-arm studies in a network meta-analysis.

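### The pooled N-of-1 model, as described, has no week level although the trigger condition is assigned by week, so week-to-week variation in AF can pass for differences between patients in their trigger effects

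*Protocol*

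**What the plan says.** **Unit of assignment.** Protocol 1.4.1 describes trigger exposure and elimination periods "with each exposure/elimination period lasting 1 week". Protocol 1.5 gives 6 periods per trigger, 3 of each kind. SAP section 2 randomises the order so that both conditions occur in every two-week block.

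**Unit of analysis.** SAP 5.4.2: "Frequency will be analyzed as a binary event on each day". Duration and severity are also daily, in a mixture model of event and non-event days.

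**Pooled model.** Protocol 1.7.2 (Meta-Analysis of N-of-1 Trials) views the data as "a multilevel structure in which a set of patients is studied with each patient having a set of measurements". It will "estimate the average effect and variance within and across patients", using a Bayesian multilevel model with non-informative priors, and will then "compare the multilevel patient estimates with those from the patient's data alone" to see how far the estimates move and how much precision is gained. SAP 5.4.3 plans one meta-analysis per trigger and takes its methods from Aim 1. For the network comparison of triggers it offers two options, of which "The first would be to treat each patient's trials as separate and introduce a common patient effect" is one.

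**Dependence over time.** For individual trials, Protocol 1.7.2 lists correlation over time as one of several candidate assumptions, to be settled by model selection. The SAP appendix, a sample-size derivation for Aim 1, has a patient effect, a patient-specific treatment effect and an error term, and assumes period effects away. It then considers constant and first-order correlation of the errors.

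**The concern.** The seven days of a week share one assigned condition. They probably share other things too, such as an illness, a poor run of sleep or an AF episode lasting several days. SAP 4.5 itself says that mood, sleep and stress could affect AF. SAP 5.4.3.3 counts days without a report as free of AF, so a lapse in app use produces a run of zeros.

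With only three weeks per condition, a patient's on-minus-off difference then varies more than 21 independent days per condition would imply. A model with patient-specific trigger effects and independent daily errors has one place to put the excess: the between-patient variance of the trigger effect.

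That variance, the improved patient estimates and their gain in precision are all named outputs of the pooled analysis. They are what a reader would use to judge whether triggers really differ from patient to patient.

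**Working it through.** The plan states no variance, ICC or precision for the pooled analysis, so there is no figure of its own to reproduce.

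**Inputs from the documents.** 3 weeks per condition and 7 days per week, so 21 days per condition and 42 per trial.

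**Assumptions.** Within-week ICC of 0.02, 0.05 or 0.10; daily AF probability 0.20, so a daily SD of √(0.20 × 0.80) = 0.40; no trigger effect in anyone; every day reported.

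**Step 1. Sampling variance of one patient's on-minus-off difference** (total daily variance set to 1).
- With week clustering: 2[ICC/3 + (1 − ICC)/21].
- With independent days: 2/21 = 0.0952.
- Ratio of the two: 1 + 6·ICC.
- Gap: 2·ICC·(1/3 − 1/21) = 0.571·ICC.

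**Step 2. Where the gap goes.** The week variance adds 2·ICC/3 = 0.667·ICC to each patient's difference. The share credited to patients is 0.571/0.667 = 6/7, or 86%.

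**Step 3. Size when the true between-patient variance is zero.** Spurious SD = 0.40 × √gap. The weight that a patient's own data keep is gap/(gap + 2/21); it should be 0.

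| ICC | True variance | Gap | Spurious SD (daily AF probability) | Weight kept |
|---|---|---|---|---|
| 0.02 | 0.1067 | 0.0114 | 0.04 | 0.11 |
| 0.05 | 0.1238 | 0.0286 | 0.07 | 0.23 |
| 0.10 | 0.1524 | 0.0571 | 0.10 | 0.38 |

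**Step 4. When patients do differ.** Take a true between-patient variance of 0.040 (SD 0.20 in daily SDs) and ICC 0.10. The two-level model estimates 0.040 + 0.057 = 0.097; simulation gave 0.100. The weight should be 0.040/(0.040 + 0.1524) = 0.21 but becomes 0.097/(0.097 + 0.0952) = 0.50. With the error taken from week means, the simulated estimate returned to 0.040.

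**Step 5. Simulation as a yardstick.** With binary daily AF, 40 patients and no effect, a 5% heterogeneity test based on day-level error rejected in about 14–15%, 36–38% and 73% of runs at the three ICCs, against about 5% with week-level error. The plan contains no such test. The rates only show how visible the inflation would be, and normal-theory tests stand in for the Bayesian fit.

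**Step 6. What is not harmed.** The average effect over P patients has variance (between-patient variance + sampling variance)/P. At ICC 0.10 the two-level model uses 0.0571 + 0.0952 = 0.1524, which is the correct total, so its standard error is about right. A simulated test of a binary modifier, with patient-specific effects fitted, rejected falsely in 4.1%, 4.9% and 4.6% of runs at the three ICCs.

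**Step 7. Would the correlation forms in the appendix help?** Correlation that is constant over all of a patient's days cancels from the on-minus-off difference. A first-order autoregressive error matched to the average correlation of adjacent days would absorb only about 22–28% of the excess when the dependence is by week.

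**The case against.** The strongest reply is that silence is not specification. The Protocol sentence is a conceptual description, not a model equation. The SAP defers to Aim 1 methods that are not supplied, and these could include a week term. The statisticians plainly know about dependence over time, since the appendix treats it for an estimator pooled across patients. SAP 4.5 plans adjustment for mood, sleep and stress where these prove related to treatment and outcome. And the analysis is secondary.

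Much of this stands. A reader might infer that the plan rules out a week term; it does not. But the structure that is described has none, and neither has the only Aim 1 model shown. That model was built for sample size, with observations a week apart, not for daily data within assigned weeks. Covariate adjustment should lower the residual ICC, but it would not remove illness, multi-day episodes or gaps in reporting.

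Two stronger readings are also tempting:
- *That the network option with a common patient effect makes the standard errors of average trigger effects too small.* That effect is there to handle correlation between different trials by the same patient. Nothing says that patient-specific trigger effects are dropped, and SAP 5.4.3 plans to report individual effects.
- *That the modifier analyses of SAP 5.4.3.2 would yield false modifiers.* Week noise is unrelated to baseline characteristics, and the simulated error rates stayed near 5%.

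**Conclusion.** The point holds as a gap in the described variance structure. Assignment is by week, analysis is by day, and no week level is shown for the pooled model. If days within a week are correlated, the two-level fit overstates the between-patient variance of the trigger effect and shrinks patient estimates too little.

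At the assumed ICCs of 0.02 to 0.10, the spurious SD of about 0.04 to 0.10 compares with a daily AF probability of 0.20. At the upper end, an imaginary one-SD difference between patients is half the base rate. With no week-to-week variation there is no bias, and the documents do not say how much to expect. The sizes rest on a normal approximation and complete daily data.

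The harm is confined to the between-patient SD, the shrunken patient estimates and their claimed gain in precision. The average trigger effect (with patient-specific effects fitted), tests of modifiers and the primary AFEQT comparison are not materially affected. The change is worth making before the data are analysed, but it does not threaten the trial's main conclusion.

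**What to change.** In the meta-analysis paragraph of Protocol 1.7.2 and in SAP 5.4.3, state a three-level model: days within assigned weeks within patients. Add a random intercept for week within patient-trial (one patient's trial of one trigger) alongside the patient intercept and the patient-specific trigger effect. Use it for AF events, duration and severity, in both the per-trigger and the network models. Report the between-patient SD and the shrunken patient estimates from that model. If the Aim 1 methods already contain such a term, write it out in SAP 5.4.3 instead of referring to it.

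The cost is one more variance term and a sentence in each document. No new data are needed, because week and assigned condition are already recorded. With 6 weeks per trial, the week variance will be estimated mainly by pooling across patients, and the intervals for heterogeneity and for individual effects will be somewhat wider.
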